12 WITHDRAWAL OF SUBJECTS

Participants will be given phone numbers for research associates and supervising physicians to call if there are adverse effects or other study-related problems. Participants will be advised that if they have any adverse effects and/or wish to stop participating in the study for any reason, they are free to do so.

Participants who are injured as a result of being in the study will have treatment available. The costs of such treatment may be covered by Roswell, depending on a number of factors.

Any participant who discontinues due to an adverse event or adverse experience (AE) must be followed until the event resolves or stabilizes. Appropriate medical care should be provided until signs and symptoms have abated, stabilized, or until abnormal laboratory findings have returned to acceptable or pre-study limits. The final status of AE will be reported in the participant's study records.

Reasons for study product(s) discontinuation/withdrawal from the study should be classified as follows:

- Death.
- Adverse side effects; related or unrelated to study product(s).
- The Investigator may discontinue a participant if, in his/her judgement, it is in the best interest of the participant to do so.
- Noncompliance: defined as missing a scheduled visit by more than 2 weeks without contact.
- Participant voluntary withdrawal. A participant may withdrawal from the study at any time, for any reason.

13 RISKS TO SUBJECTS

The potential risks to participants in the clinical studies, and their likelihood and seriousness, are described below

- Nicotine overdose: Some people who use nicotine products may experience symptoms of nicotine overdose such as nausea, sleep disturbance, headache, and vomiting; however, these symptoms are usually mild and temporary. Before nicotine products are used in human participants, they have undergone laboratory testing to assess the yields of nicotine present in the products; this will also provide quality control information to select the safest product.
 - The studies using nicotine products in participants will be performed in a clinical setting accustomed to monitoring for adverse events. The Principal Investigator and Co-Investigators have considerable experience with conducting outpatient studies

on novel nicotine delivery devices and their effects on participants and will be able to provide appropriate safety monitoring.

- Participants will be instructed that the investigational products are not to be ingested. If a product is ingested by mistake, the participants will be instructed to call the study physician [contact]). If they are experiencing serious symptoms of nicotine overdose, the participant should contact Poison Control or Emergency Medical Services.
- Nicotine withdrawal: Many individuals who quit smoking exhibit a pattern of symptoms related to withdrawal from tobacco use. These symptoms include: sadness and anxiety, irritability, anger, difficulty concentrating, appetite change and weight gain, insomnia, and decreased heart rate. Because participants in the studies will be asked to refrain from smoking overnight, it is likely that they will experience some of these symptoms. Consent forms will include sections describing the possibility of this occurrence. Study personnel will be trained to recognize these symptoms and educate the participants about them.
- Respiratory irritation: Some people who use ENDS (Electronic Nicotine Delivery Systems) may experience irritation of the mucosal membranes of the upper respiratory tract, but this may not be likely as they are already cigarette smokers. We will exclude participants or postpone procedures if they demonstrate chronic or acute respiratory problems.
- Inconvenience: It is possible that participants will experience inconvenience due to multiple study visits required.
- Emotional distress: Participants may experience psychological discomfort during assessments when discussing feelings and attitudes about smoking and using nicotine products, or from learning about the risks of smoking. However, all participants will be current smokers and we do not expect this type of reaction to be likely. Study personnel will be alerted to expect this from a small number of participants and will be trained to make referrals for mental health services as needed. Personnel will be trained to query for adverse emotional reactions during assessments and will be trained to deal with such reactions and to provide additional referrals if needed. In addition, if assessments indicate psychiatric concerns, referrals to appropriate psychological services will be provided.
- Reproductive Risks: Women will be advised to notify the study staff if they become or intend to become pregnant during the study period. Because nicotine and ENDS vapor safety for an unborn baby is unknown, participants will be told that they should not become pregnant while on this study nor should they nurse a baby. If a woman is pregnant or breastfeeding, she may not participate in this study, and if she becomes pregnant during the study, she will be removed from the study.

As general measures to minimize the likelihood of participants experiencing these side effects, staff will have the study physician's cell phone number and will contact the study physician with all questions and concerns. We will also:

- Enroll participants in self-reported good general health
- Administer products of high quality.
- Monitor self-reported side effects at each study session. Participants will be informed about the potential for adverse events or side effects, including respiratory/oral irritation, cough,

Roswell Park Protocol No.: I-3234822

phlegm, headache, nausea, and emotional distress from learning about the adverse health consequences of smoking. Participants will be told that they should proceed with caution until they are certain that the study products do not affect their performance.

- The study physician will be alerted to any severe side effects or any reported adverse events. The study physician will review the information provided by the research staff and if applicable, will contact the study participant within 24 hours of being notified to gather more information and determine the appropriate course of action for the participant. Ultimately, the study physician will decide if the adverse event is related to study treatment and whether the participant should discontinue its use.

Participants will be told that they should proceed with caution when using study products and to report any adverse symptoms or side effects to study personnel immediately.

14 POTENTIAL BENEFITS TO SUBJECTS

There is no direct benefit for those who decide to participate and enroll in this study.

15 DATA AND SPECIMEN BANKING

Samples Collected at Roswell Park:

All samples will be immediately transported to the Health Behavior Department Laboratory (Roswell Park Comprehensive Cancer Center). Saliva samples will be centrifuged for 2 minutes prior to storage. All samples will immediately be frozen at -20°C or below in [name] until analyzed (unless otherwise noted above). Female urine samples will be tested for pregnancy. All sample results are recorded in logs and kept in:

[name]
Gratwick Basic Science Building (GBSB)
Health Behavior Department Laboratory
Laboratory location: 4th Floor, Room 4942
Laboratory [contact]
[name] office number: [contact]

If there are remaining samples after all analysis has been done and the participant checks "YES" on the consent document to having any extra samples stored for future studies, then the samples will be kept in a -20°C or below freezer in [name] Laboratory listed above. If there are remaining samples and the participant checks "NO" on the consent document to having any extra samples stored, then the extra samples of that participant will be immediately destroyed once they are taken off study or analyses are completed. Any future research on the remaining samples will only be done under IRB approved protocols.

EXTERNAL SITES: Follow directions above for sample collection and processing. The cryogenic tubes will be labeled with the participant identification number (Participant ID, PID) (unique to external-site participants), initials, the participant's study number, clinical study number, protocol time point, and protocol day. The saliva samples will immediately be refrigerated or frozen at -20°C or below (samples are to be stored until requested for batch mailing).

Frozen samples will be shipped via Fed Express Overnight on dry ice with delivery on Mon-Fri. NO SATURDAY DELIVERY. Do not ship on a Friday or the day before a holiday.

Roswell Park Protocol No.: I-3234822

Address shipments and any questions regarding specimen processing to:
[contact], [contact].

Note: All investigator or analyzing research laboratories housing research samples need to maintain current **Temperature Logs** and study-specific **Sample Tracking and Shipping Logs**. The Principal Investigator/Laboratory Manager **must** ensure that the stated lab(s) have a process in place to document the receipt/processing/storage/shipping of study-related samples/specimens. This is required for both observational and interventional clinical studies collecting clinical samples.

Data Banking

For the purposes of this research, we will collect the following identifiable information: Participant name (to verify identification), date of birth (to verify age), telephone number and email address (to facilitate contact for scheduling). Identifiable information will be retained in a separate Excel file from the analytic dataset. The only link to identifiable information will be via a unique ID number.

All questionnaires are administered via REDCap, housed at RPCI or URMIC. All data files will be electronic, including only the unique subject ID. At study completion, datafiles from RPCI and URMIC will be combined and will be stored on the Cancer Prevention server (\CancerPrev\CancerPrev\$\HealthBehavior). Access to the folder is restricted to authorized users. Standard protocols for data encryption when using laptops and USB drives will be followed.

Any clinical data that is associated with the samples, will be stored on a secure server in the Department of Health Behavior, will be accessible only by the PI, Co-Investigators and PI designated data manager and, will be password protected. All computer entry and networking programs will be done using PIDs only. Any clinical data and/or specimens for future research will require verification of an IRB-approved protocol and will be de-identified before being released.

Note: All investigator or analyzing research laboratories housing research samples need to maintain current Temperature Logs and study-specific Sample Tracking and Shipping Logs. The Principal Investigator/Laboratory Manager must ensure that the stated lab(s) have a process in place to document the receipt/processing/storage/shipping of study-related samples/specimens. This is required for both observational and interventional clinical studies collecting clinical samples.

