Saliva samples will be collected before and after product use in both session using a Salimetrics SalivaBio Passive Drool method (https://salimetrics.com/collection-method/passive-drool-salivacollection_ device/). This method involves unstimulated collection of whole saliva which will be passively drooled into a cryovial until ~1.8mL of saliva is collected. Samples will be divided into aliquots and frozen at -20 C. Saliva will be tested for nicotine using a GC-qTOF-MS method. Saliva will be further tested for stress markers of cortisol (<https://salimetrics.com/assay-kit/salivary-cortisol-elisa-kit/>) and DHEA (<https://salimetrics.com/assay-kit/salivary-dhea-elisa-kit/>) and proinflammatory cytokines of IL-6 (<https://salimetrics.com/assay-kit/salivary-il-6-elisa-kit/>) and IL-1b (<https://salimetrics.com/assaykit/salivary-interleukin-1-beta-elisa-kit/>). Color intensity will be read at 450nm using a plate reader (BioTek). The integrated values of known standards will be used to generate a standard curve. Density values for unknown samples will be determined by interpolation from the standard curve for each analyte to calculate concentrations in pg/mL saliva. Saliva samples may also be used to test for nicotine and cotinine levels using similar methods to blood analyses. Additional details about the processing of saliva samples are

Roswell Park Protocol No.: I-3234822

provided in **Section 15**. A full description of the sample collection procedure can be found in **Appendix D**.

Optional Oral Rinse Sample (Roswell Park site only)

Oral rinse samples will be collected using a rinse & gargle method with Scope mouthwash, which will be stored in a -80°C freezer and kept at Roswell Park for analysis. We will characterize the microbiota by analyzing 16S rRNA (bacteria) and ITS1 gene (fungi) and the virome (including human papillomaviruses) using NGS. We will also complement analyses with functional information obtained through Bioinformatic algorithms (PICRUSt) and shotgun metagenomics. This approach will quantify differences in secreted and other microbial gene products; connect them to annotated pathways and make them available for downstream analyses. Thus, we will analyze inferred biochemical functions that are related to inflammation and subsequent oral and respiratory outcomes. Additional details about the processing of oral cell samples are provided in **Section 15**. A full description for oral rinse sample collection is provided in **Appendix D**.

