16 MEASUREMENT OF EFFECT

Nicotine boost will be measured as the post-bout saliva nicotine concentration minus the pre-bout saliva nicotine concentration.

Subjective questionnaires are scored on a 0-100 visual analog scale (some exceptions, such as -100 to 100) or a Likert scale (varying amount of points). Subjective responses will be evaluated based on their change from pre- to post-bout and for differences between products.

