Appendix D Sample Collection Procedures

Saliva Sample

Step 1. Open foil pouch and remove the Saliva Collection Aid (SCA)

Step 2. Place ribbed-end of the SCA securely into a pre-labeled collectionvial

Step 3. Allow saliva to pool in mouth. Then, with head tilted forward, gentlyforce saliva through the SCA into the vial. Fill to required volume.

Step 4. Remove and discard SCA. Attach cap to collection vial and tighten

Step 5. After collection, freeze samples at or below -20°C.

Step 6. For Analysis, follow Salimetrics SOP for corresponding ELISA kit.

OPTIONAL Oral Rinse Sample (collected at Roswell Park only)

Supplies:

SCOPE® mouthwash: Travel size Scope mouthwash bottle is used to rinse mouth.

Saline solution: An alternative to Scope mouthwash, it will be used for participants with openoral ulcers or in recovering alcoholics concerned about the alcohol content.

Medicine cup: A 4.5 oz. sterile medicine cup used for pouring in the mouthwash.

Specimen container: A 5 oz. sterile specimen container used for spitting in the mouthwash andfor storing.

Gloves: The dental examiner will use a new pair of gloves before the exam begins.

Procedure:

1. Put on gloves and ask the participant: *“Do you have any sores in your mouth that might hurtwhen you use a mouthwash with some alcohol in it, such as Scope?”*

2. Pour 10mL of SCOPE® mouthwash, or the alternative saline solution, into a medicine cup,making sure not to touch the rim of the cup.

3. Hand the medicine cup with the mouthwash to the participant and explain to the participant: *“We are going to ask you to swish some Scope mouthwash around your mouth, gargle, and then spit the mouthwash into a cup. First, you will rinse your mouth with the mouthwash for 5 seconds and then gargle for 5 seconds. You will do this three times and then spit the mouthwash into a cup. Do you have any questions about this test?”*

Roswell Park Protocol No.: I-3234822

4. Have the participant put the mouthwash, or saline, into their mouth when ready and then instruct them through the swish gargle cycles using a timer.
5. At the end of the 30 seconds, open the specimen container and hand it to the participant. Hold the top lid down to avoid contaminating it.
6. Have the participant spit the mouthwash into the specimen container when done gargling. Participants are allowed to touch the rim of the container when they spit the mouthwash.

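### The external site may refrigerate saliva with no temperature or time limit, while every other saliva instruction in the protocol requires freezing at -20°C or below

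*Combined protocol and SAP*

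**What the plan says.** Four places deal with keeping saliva after collection.

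- Section 11.4, Saliva Samples, no site distinction: "Samples will be divided into aliquots and frozen at -20 C".
- Section 15, samples collected at Roswell Park: "All samples will immediately be frozen at -20°C or below".
- Appendix D, Step 5, no site distinction: "After collection, freeze samples at or below -20°C".
- Section 15, external sites: "The saliva samples will immediately be refrigerated or frozen at -20°C or below (samples are to be stored until requested for batch mailing".

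The external-site paragraph opens with "EXTERNAL SITES: Follow directions above for sample collection and processing" and goes on to shipping: "Frozen samples will be shipped via Fed Express Overnight on dry ice with delivery on Mon-Fri".

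The samples serve two purposes. Section 16 defines an outcome from them: "Nicotine boost will be measured as the post-bout saliva nicotine concentration minus the pre-bout saliva nicotine concentration". Section 11.4 adds further assays: "Saliva will be further tested for stress markers of cortisol", with DHEA, IL-6 and IL-1b alongside. Section 8 lists none of these as an endpoint, and Section 19 gives no analysis for them.

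**The concern.** One protocol holds two storage rules for the same kind of specimen. Taken at its ordinary meaning, the external-site sentence lets staff put saliva in a refrigerator and leave it there until a batch is called for. The shipping line governs the state of the sample at dispatch, not how long it sat unfrozen beforehand.

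At stake is the comparability of the saliva results. If an analyte is lost in the refrigerator, levels from the two sites would not mean the same thing. A difference between two samples from one session would be wrong if the two were kept differently or for different times. Loss in storage cannot be undone after assay. Without a record of storage condition and time, the affected samples could not be picked out.

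**Working it through.** **Step 1: the instructions side by side.**

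| Place | Applies to | Freezing required? | Refrigeration allowed? | Limit on unfrozen time |
|---|---|---|---|---|
| Section 11.4 | all saliva | yes | no | none stated |
| Section 15, Roswell Park | Roswell Park | yes, at once | no | immediate |
| Appendix D, Step 5 | all saliva | yes | no | after collection |
| Section 15, external sites | second site | one of two options | yes | none until batch mailing |

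The external-site sentence is the only one that offers refrigeration. The instruction to follow the earlier directions, and the reference to frozen shipments, conflict with that option but do not withdraw it.

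**Step 2: how many samples.** Table 1 gives three saliva samples per session: one at the start and one after each of two bouts. Section 19.1 gives expected completers by session. Its two constant-rate rows reproduce as 72 × 0.95^(k−1) and 72 × 0.90^(k−1) for session k, rounded. At session 7 these are 52.9 and 38.3, shown as 53 and 38.

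- 5% attrition: 72 + 68 + 65 + 62 + 59 + 56 + 53 = 435 sessions; × 3 = 1,305 samples.
- 10% attrition: 72 + 65 + 58 + 52 + 47 + 43 + 38 = 375 sessions; × 3 = 1,125 samples.
- Mixed row: 72 + 68 + 65 + 58 + 53 + 47 + 43 = 406 sessions; × 3 = 1,218 samples.

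The split between sites is not given. Assuming one third to one half at the external site, the range runs from 1,125 / 3 = 375 to 1,305 / 2 = 652.5, or about 375 to 650 samples.

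**Step 3: a loss shared by all external-site samples.** Let r be the fraction of analyte recovered and f the share of participants at the external site. Measured boost there is r × post − r × pre = r × (true boost). A product contrast pooled over sites is then 1 − f(1 − r) of its true value. The documents give neither r nor f, so these values are illustrations only:

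| r (assumed) | f = 1/3 | f = 1/2 |
|---|---|---|
| 1.00 | 1.000 | 1.000 |
| 0.95 | 0.983 | 0.975 |
| 0.90 | 0.967 | 0.950 |
| 0.80 | 0.933 | 0.900 |

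The contrast shrinks but does not change sign.

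**Step 4: handling that varies among one participant's samples.** If only the post-bout tube loses a fraction (1 − r), boost is too low by (1 − r) × post. If only the pre-bout tube does, boost is too high by (1 − r) × pre. Neither cancels. Two features of the design bear on this.

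- Table 1 and Appendix E show no separate sample before bout 2, so the middle tube appears to serve as the end of bout 1 and the start of bout 2. If that tube alone loses an amount d, boost 1 falls by d, boost 2 rises by d, and boost 2 minus boost 1 moves by 2d. Bout order is randomized, so across participants this would tend to add noise rather than a consistent shift between ad lib and directed bouts.
- Own-brand liquid is always Session 1 (Sections 11.3 and 19.2). If tubes wait for a batch, those from Session 1 could wait longest, and a time-dependent loss would line up with own-brand versus study liquid. Order within Sessions 2-5 and within Sessions 6-7 is randomized, so comparisons inside those blocks are better protected.

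**The case against.** The strongest case on the other side has four parts.

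- **The rest of the text points to freezing.** External sites are told to follow the earlier directions, two general procedures require freezing, and only frozen shipment is described. The sentence can even be read as refrigerated or frozen, both at -20°C or below. It is fair to say that freezing is probably intended. But the site-specific sentence still grants the option, and if the narrower reading is meant, the extra words do nothing and can go.
- **Records already exist.** Section 15 requires temperature logs and sample tracking and shipping logs. This stands in part: storage should be traceable. Time from collection to freezer is not named as an item to record.
- **The reach is small.** This stands. Saliva measures are not endpoints in Section 8 and have no analysis in Section 19. Participants complete all conditions, so product comparisons are within person and within site.
- **No harm is shown.** This also stands. A reader might infer that stability does differ by site, that staff choose tube by tube so that pre- and post-bout samples are kept differently, or that refrigeration lasts for weeks. The documents support none of these as fact. They contain no stability or recovery data, do not say the external site refrigerates, and do not say at what level the choice is made. A reader might also infer that a site effect would be confounded with degradation, but no between-site comparison of saliva results is planned.

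**Conclusion.** The inconsistency is real and worth correcting, within limits. The protocol permits a difference in handling; it does not show a difference in stability. What may be affected is nicotine boost and the cortisol, DHEA, IL-6 and IL-1b results. The topography, sensory and drug-liking endpoints do not depend on saliva.

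The size of any loss is unknown. A uniform loss at one site would mainly weaken boost contrasts: under the assumed recoveries of 0.80 to 1.00 and shares of one third to one half, 90% to 100% of the true contrast remains. Uneven handling or holding time could do more, because it does not cancel, but whether it occurs cannot be told from the documents.

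The exposed count of about 375 to 650 samples rests on the plan's own attrition table and the assumed site split. The full-completion maximum of 3 × 7 × 72 = 1,512 should not be used as the base, since the plan itself expects dropout.

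**What to change.** In Section 15, external sites, delete the words 'refrigerated or', so that saliva is frozen at once at -20°C or below and stays frozen until batch shipment. One rule then holds at both sites and agrees with Section 11.4 and Appendix D.

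Add collection-to-freezer time to the tracking logs that Section 15 already requires. Flag any sample already held refrigerated, with its holding time where known. In any saliva analysis that is carried out, report results with and without the flagged samples.

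The external site must already ship frozen on dry ice, so the storage rule itself should add little burden. The cost is a short protocol edit with notice to the site, one more logged time per sample, a look back at samples already taken, and one sensitivity check.
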